10.6 Study Period and Visit Window Definitions

Unless otherwise specified, data for regular scheduled visits will be summarized.

Table 8. Visit Window

Visit Name	Actual Time Point	Visit Window
Screening	~ -Week 2	-
Cycle 1 Day 1	Day 1	-
Cycle 1 Day 15	Day 15	±3 days
...		
Cycle Z Day 1	Day (28×Z + 1)	±3 days
Cycle Z Day 15	Day (28×Z + 15)	±3 days
End of Treatment (EOT)	-	±7 days
Post Treatment Follow-Up	EOT + 28 days	±7 days
Survival Follow-Up	Every 8 weeks after Post-Tx F/U	±7 days

10.7 Software for Statistical Analysis

SAS® Version 9.4 or higher (SAS institute, Cary, NC, USA)

11. DATA HANDLING COVENTIONS

11.1 Handling of Missing Data

11.1.1 Missing Value of Efficacy Variables

If any value is missing at any time point or a subject was withdrawn prior to study completion so that there are no data, they will be handled as missing without imputation.

11.1.2 Missing Value of Safety Variables

For safety endpoints, observed data will be used for analysis without imputation of missing values.

11.2 Repeated or Unscheduled Assessments

In case there are measurements from an unscheduled visit after the first dose of the investigational product, measurements at scheduled and unscheduled visit are chronologically presented in the subject list whereas summary of descriptive statistic by time point will only include measurements at scheduled visits.

11.3 Handling of Incomplete Date

For AE data, in case day or month is omitted from the start date, only collected date units will be used without any imputation of date.

When the entire start date is missing or the format of the collected AE date does not allow for comparison, the AE will be assumed to be TEAE.

For surgeries/procedures, in case day or month is omitted from the date thus collected as 'UK', only collected date units will be used without any imputation of date. When the entire date is missing or the format of the collected date does not allow for comparison with the first IP administration date, the surgeries/procedures are assumed to be used prior to the first dose administration date of the investigational product. When the format of the collected date does not allow for comparison with the EOT date, the surgeries/procedures are assumed to be used on or before the EOT date.

For medication, in case day or month is omitted from the start or end date thus collected as 'UK', only collected date units will be used without any imputation of date. When the entire start date is missing or the format of the collected start date does not allow for comparison with the first IP administration date, the medication is assumed to be used prior to the first dose administration date of the investigational product. When the format of the collected start date does not allow for comparison with the EOT date, the medication is assumed to be used on or before the EOT date. In case end date is missing or format of the collected end date does not allow for comparison, medications assumed to be 'ongoing'.

12. INDEPENDENT DATA MONITORING COMMITTEE (IDMC) AND INTERIM ANALYSIS

12.1 IDMC

Independent data monitoring committee (IDMC) is composed of 3 members (2 clinicians and 1 statistician) who are fully independent of the entity conducting the trial. The IDMC should comply with IDMC charter in the ICH GCP guideline.

The IDMC will meet at least once prior to trial initiation (organizational meeting) and then at least three additional times at specific milestones (one for the formal interim analysis and two for the safety review) in the trial. The detailed schedule and purpose of the IDMC meetings is described in IDMC charter.

For the formal interim analysis, the IDMC will convene when approximately 163 events are observed to review unblinded results of the interim analysis. The IDMC can convene when unexpected adverse drug reaction with a Grade 3 or more (based on NCI-CTCAE 4.03) are observed. The IDMC can also convene, if necessary, to ensure appropriate review of the Japan specific safety run-in (Sec 3.5).

12.2 Interim Analysis and Stopping Rules

The interim analysis for futility will be conducted with collected clinical data when approximately 163 (approximately 50% of the required 325 events) events are observed. The independent contract research organization for the interim analysis (AXIO Research, LLC) will conduct all the interim analysis for the study. All planned study procedures such as subject enrollment, treatment and follow-up visit should be performed regardless of the interim analysis. If it is necessary to change the timing of the interim analysis, in consultations with sponsor, the IDMC can change interim analysis time and its corresponding statistical criteria for early termination.

The interim analysis for futility will assess the primary (OS) and key secondary (PFS, ORR) efficacy endpoints using the statistical methods planned for the final analysis but only for ITT population. The interim analysis for futility and two safety reviews will assess adverse events and safety endpoints. The IDMC will review the results of the interim analysis and recommend to the sponsor whether or not to terminate the trial for futility. Final decision regarding study termination will be made by the sponsor.

The IDMC and independent statisticians involved in the interim analysis should keep the interim analysis result completely confidential. The results of the interim analysis should be kept unknown to all staff involved in the conduct of the trial. If early termination is decided, the IDMC delivers the interim analysis report to the sponsor after the official unblinding procedure.

Early termination will be considered if the interim analysis is futile, that is when the calculated conditional power based on primary efficacy endpoint, overall survival (OS), is less than 0.2. The main/official futility analysis will assume future data is distributed as the current data to calculate conditional power (Pepe-Anderson-Betensky test). For additional sensitivity check, conditional power will be calculated assuming future data are distributed according to the alternative hypothesis, specifically hypothesized effect of HR=0.72 (Lan-Simon-Halperin test).

Early stopping for futility interim analysis does not inflate the Type-I error, thus Type I-error adjustment is not needed.

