#### 8.4.2. Interim Analysis

An interim analysis will be conducted with collected clinical data when approximately 163 (approximately 50% of the required 325 events) events are observed. All planned study procedures such as patient enrollment, treatment and follow-up visit should be performed regardless of the interim analysis. If it is necessary to change the timing of the interim analysis, in consultations with sponsor, the IDMC can change interim analysis time and its corresponding statistical criteria for early termination.

The interim analysis will assess the primary efficacy endpoint. The IDMC will review the results of the interim analysis and recommend to the sponsor whether or not to terminate the trial for futility. Final decision regarding study termination will be made by the sponsor.

The IDMC and statisticians involved in the interim analysis should keep the interim analysis result completely confidential. The results of the interim analysis should be kept unknown to all staff involved in the conduct of the trial. If early termination is decided, the IDMC delivers the interim analysis report to the sponsor after the official unblinding procedure.

Early termination will be considered if the interim analysis is futile, that is when the calculated conditional power based on primary efficacy endpoint is less than 0.2. Early stopping for futility interim analysis does not inflate the Type-I error, thus Type I-error adjustment is not needed.

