7.5 Efficacy Analysis

7.5.1 Multiple Comparison Procedure on Primary and Key Secondary Endpoints

To control the family-wise error rate (FWER) on testing multiple hypotheses of interest, the fixed sequence closed testing procedure will be used. In this fixed sequence procedure, each hypothesis will be sequentially tested with two-sided 5% level only if higher level hypothesis is rejected. For this fixed sequential testing, the primary and key secondary efficacy endpoints will be tested using the ITT set. Specifically,

1. Test OS with two-sided 5% level
2. If OS is significant, test PFS (based on central review) with two-sided 5% level
3. If OS and PFS are significant, test ORR (based on central review) with two-sided 5% level

If a prior test is not statistically significant, then the subsequent analyses will be exploratory rather than confirmatory.

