7.5.2 Primary Efficacy Analysis

- Overall Survival (OS): Time from randomization to death. Subjects alive or lost to follow-up are censored at the date the subject was last known to be alive.

The primary efficacy endpoint (OS) will be analyzed using ITT, FAS and PPS. The primary efficacy analysis will be conducted using the ITT set. The final analysis will be conducted when approximately 325 events are observed.

The comparison of OS between the two treatment groups will be performed with a logrank test stratified on the randomization stratification variables Geographic region (Asia vs. North America/Europe), Prior

ramucirumab treatment (Yes vs. No), and Treatment therapy line (3rd vs. ≥ 4th) at the two-sided alpha=0.05 level of significance.

In order to estimate the hazard ratio, a Cox proportional hazards regression model will be fitted with treatment group as a factor and the randomization stratification variables [Geographic region (Asia vs. North America/Europe), Disease measurability (measurable vs. nonmeasurable), Prior ramucirumab treatment (Yes vs. No), and Treatment therapy line (3rd vs. ≥ 4th)] as covariates. The hazard ratio and its 95% confidence interval will be presented.

Kaplan-Meier estimates will be calculated for each treatment group to construct the survival curve. The median overall survival and its 95% CI (based on Greenwood formula) will be presented. The primary endpoints will also be analyzed using the FAS and PPS.

Data will be summarized in the following tables and figures.

-Table. Overall Survival – ITT

-Table. Overall Survival – FAS

-Table. Overall Survival – PPS

-Figure. Kaplan Meier Plot for Overall Survival – ITT

-Figure. Kaplan Meier Plot for Overall Survival – FAS

-Figure. Kaplan Meier Plot for Overall Survival – PPS

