13. CHANGE FROM PROTOCOL

Protocol v5.0 Location(s)	SAP Location(s)	Protocol v5.0 Language	SAP Language Changed from Protocol v5.0	Reason of Change
Section 8.1.1 p.73	Section 3.7.1 p.15	"Where HR (hazard ratio) is the ratio of median overall survival of Placebo and Rivoceranib* group."	"where HR (hazard ratio) is the ratio of median overall survival of denotes the hazard ratio for Rivoceranib group relative to Placebo group. "	Clarify language in the protocol.
Section 8.1.3 p.74	Section 3.7.3 p.16	"325 events (413 subjects) are needed."	" a total of 325 events (413 subjects) are needed to provide approximately 80% power for Overall Survival. "	Clarify language in the protocol.
Section 8.3.2 p.75	Section 4.1 Section 4.2 Section 4.3 Section 4.4 p.17	"ITT set consists of data from all subjects who are randomized." "The analysis for primary endpoint, OS and the secondary endpoints of PFS and ORR will be conducted in the ITT set." "Safety set consists of data from all subjects who received at least one dose of Rivoceranib or placebo." "The FAS will be used for all efficacy analyses." "The PPS will be used for all efficacy analyses."	"ITT set consists of data from all subjects who are randomized into the study. " " The analysis The ITT set will be used for the primary efficacy analyses endpoint, OS and the secondary endpoints of PFS and ORR will be conducted in the ITT set. " "Safety set consists of data from all subjects in the ITT population who received at least one dose of Rivoceranib or placebo." "The FAS will be used for all supportive efficacy analyses." "The PPS will be used for all supportive efficacy analyses."	Clarification that ITT set will be used for the primary efficacy analyses, and FAS and PPS will be used for supportive efficacy analyses.

Protocol v5.0 Location(s)	SAP Location(s)	Protocol v5.0 Language	SAP Language Changed from Protocol v5.0	Reason of Change
Appendix 2: Table 3 p.91	Section 5.1 Table 4 Table 5 p.18	Table title: Time Point Response	Table title: Time Point Response (subjects with target and non-target lesion) Added table 5: Time Point Response (subjects with non-target lesion only)	Clarified on the original table and added a table to define response for subjects with non-target lesion only.

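### The stated 80% power for overall survival is the no-interim figure; if the official futility criterion is always followed, power at HR 0.72 is about 74–75%.

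*SAP*

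**What the plan says.** SAP section 13, quoting the new wording of SAP 3.7.3, ties 325 events (413 subjects) to the power claim: the events are needed "to provide approximately 80% power for Overall Survival". No condition is attached.

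SAP 12.2 plans one futility look at about 163 deaths, roughly half of 325. "Early termination will be considered if the interim analysis is futile", meaning that conditional power for OS is below 0.2; protocol 8.4.2 uses the same threshold ("when the calculated conditional power based on primary efficacy endpoint is less than 0.2"). The SAP then fixes the assumption behind it: "The main/official futility analysis will assume future data is distributed as the current data to calculate conditional power". A second calculation, under the design alternative ("specifically hypothesized effect of HR=0.72"), is only a sensitivity check. The rule is advisory: the IDMC recommends, and "Final decision regarding study termination will be made by the sponsor".

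The readable interim text in both documents addresses the effect of the look on type I error, where it correctly says no adjustment is needed. It does not address the effect on power. Protocol 8.1 and SAP 3.7 are blacked out and cannot be checked.

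**The concern.** A futility look cannot inflate type I error, but it can cost power, because some trials stopped at the interim would have been significant at the end. Projecting the current trend makes the cost appreciable: at half the information the interim estimate is noisy, and an unlucky first half is carried forward into the second.

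The sponsor and IDMC have discretion over whether to act. To use it well they need two numbers: how often the criterion is met when the drug has exactly the planned effect, and how much power remains if they act on it. The unqualified 80% supplies neither. It is also the power figure that readers of the trial will rely on for the primary endpoint.

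**Working it through.** **Inputs**
- Final analysis at 325 deaths; stated power about 80% (SAP 13, wording of 3.7.3).
- Design effect HR 0.72 (SAP 12.2).
- 2:1 allocation (SAP 3.1), so the information per death is (2/3)(1/3) = 2/9.
- "Test OS with two-sided 5% level" (SAP 7.5.1): critical value 1.960, not adjusted for the look.
- Interim at 163 deaths: t = 163/325 = 0.5015, √t = 0.708, √(1−t) = 0.706.
- Criterion: current-trend conditional power below 0.2 (SAP 12.2).

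**1. Reproduce the plan's figure with no look (Schoenfeld)**
- Drift = |ln 0.72| × √(325 × 2/9) = 0.3285 × 8.498 = 2.792.
- Power = Φ(2.792 − 1.960) = Φ(0.832) = 79.7%.
- Deaths for 80% = (1.960 + 0.842)² / [(2/9)(ln 0.72)²] = 327.3, so 328.

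Other 80%-power calculations do not fit 325: Schoenfeld 1:1 gives 291, Freedman 1:1 gives 297, Freedman 2:1 gives 298, and a one-sided 5% test at 2:1 gives 258. The stated figure matches the fixed 2:1 two-sided design.

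**2. Turn the criterion into an observed HR**
- Current-trend CP = Φ[(Z1/√t − 1.960)/√(1−t)].
- CP < 0.2 when Z1 < √t × [1.960 − 0.842√(1−t)] = 0.708 × 1.366 = 0.967.
- Boundary HR = exp(−0.967/√(163 × 2/9)) = exp(−0.967/6.018) = 0.852.

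**3. Chance of meeting it at HR 0.72**
- Mean of Z1 = 2.792 × 0.708 = 1.977.
- P(Z1 < 0.967) = Φ(−1.010) = 15.6%.

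**4. Power if it is always followed**
- P(Z1 ≥ 0.967 and Z2 > 1.960), bivariate normal with correlation √t, = 73.9%.
- Loss = 79.7 − 73.9 = 5.9 points (unrounded 5.87). Of the 15.6% that meet the criterion, 5.87/15.63 = 38% would have been significant at 325 deaths; the other 62% would have ended negative anyway.

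**5. Sensitivity**
- Look at 150 to 175 deaths: always-followed power is 73.1% to 74.5%.
- True HR 0.75: power falls from 68.6% to 62.4%.
- To keep 80% power with the rule always followed, about 379 deaths would be needed.

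**6. Log-rank simulation**

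Assumptions: uniform accrual, exponential survival, no dropout, unstratified test, looks at 163 and 325 deaths, 10,000 runs each. Accrual of 9 and 21 months is from SAP 3.2. Control medians of 4.7 and 3.8 months are the placebo results of the earlier apatinib phase III study and the ramucirumab monotherapy study (protocol 1.2 and 1.1).

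| N | Accrual (months) | Control median (months) | No look | Criterion met | Always followed |
|---|---|---|---|---|---|
| 459 | 21 | 4.7 | 80.9% | 14.8% | 75.3% |
| 459 | 9 | 4.7 | 80.7% | 15.0% | 75.0% |
| 413 | 9 | 4.7 | 81.1% | 14.9% | 75.1% |
| 459 | 21 | 3.8 | 80.9% | 14.9% | 75.0% |

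Two further runs of 4,000 trials (459 patients, median 4.7 months) gave 80.4% falling to 74.3% with 9-month accrual, and 81.3% falling to 76.2% with 21-month accrual. The loss is 5 to 6 points throughout.

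**7. The two planned calculations side by side**
- At the official boundary, conditional power under HR 0.72 is Φ[(0.967 × 0.708 + 2.792 × 0.4985 − 1.960)/0.706] = Φ(0.165) = 57%, beside 20% on the current trend.
- Used as the rule, the HR 0.72 version would trigger at Z1 < −0.036 (HR above 1.006). It would be met in 2.2% of trials at HR 0.72 and leave power at 79.5%. Under no effect it would be met in 49% of trials, against 83% for the official version.

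**The case against.** No stated figure is wrong on its own terms: 79.7% is approximately 80%, and the rule does not oblige anyone to stop. On this view, 74% is a floor reached only by mechanical obedience, and the planned HR 0.72 calculation already warns of a borderline case. Overrides would probably fall near the boundary. If the IDMC stopped only when Z1 was below 0.56, power would be 77.7%; if it stopped only when both calculations were below 0.2, power would be 79.5%. This stands, and it is why the 74–75% must be stated as conditional on always following the criterion. It does not rescue an unqualified 80%, because the version that costs power is the one the SAP makes official.

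Three narrower points also have force:
- The redacted sample-size sections, or the IDMC charter that SAP 12.1 cites, may already give these figures. No omission is alleged.
- Normal approximation and simulation differ by a point or so, so the text should name the method or give a range.
- The interim may already be past. With 459 patients, 21-month accrual and a 4.7-month control median, 163 deaths fall about 14 months after the first randomisation. From the planned January 2017 start, that is before protocol 5.0 of November 2018, which this SAP cites. SAP 12.2 is in the future tense and the actual date is not given, so this is a doubt only.

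**Conclusion.** The concern holds. The approximately 80% power is the figure for a design with no interim look. At HR 0.72 the official criterion is met in about 15–16% of trials. Always following it reduces power by about 6 points: from 79.7% to 73.9% by normal approximation, and from about 81% to about 75% in the 10,000-run log-rank simulations. If it is sometimes overridden, power lies in between; overriding half the time regardless of the interim result gives 79.7 − 0.5 × 5.87 = 76.8%.

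This rests on HR 0.72 being the design effect (SAP 12.2 calls it hypothesized, and it reproduces 325 deaths), proportional hazards, and conditional power computed as the SAP words describe it. If the software instead added one standard error to the current estimate before projecting, the criterion would be met in about 6.6% of trials and power would be 78.2%, but that is not what the SAP sentence says. The planned test is stratified ("The comparison of OS between the two treatment groups will be performed with a logrank test stratified on the randomization stratification variables"), whereas the simulations were not; the effect is probably small. The analysis itself is not invalidated.

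**What to change.** Beside the stopping rule in SAP 12.2, and with the power statement in SAP 3.7.3, state that 325 deaths give about 80% power at HR 0.72 if the futility criterion is not acted on; that power is about 74% (normal approximation; about 75% by log-rank simulation) if it is always followed; and that the criterion is met in about 16% of trials at HR 0.72 (about 15% by simulation). If the redacted text or the IDMC charter already says this, a cross-reference is enough. Give the IDMC the same figures before the interim; if the interim has taken place, record them in the SAP.

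No change of rule is asked for. Making the HR 0.72 version official would recover almost all the power but would stop far fewer ineffective trials, and that trade-off is for the sponsor and IDMC.

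The cost is one SAP sentence and one line of IDMC material. There are no extra patients and no change to the test or analysis sets. The restated power is less favourable.

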13. CHANGE FROM PROTOCOL

Protocol v5.0 Location(s)	SAP Location(s)	Protocol v5.0 Language	SAP Language Changed from Protocol v5.0	Reason of Change
Section 8.1.1 p.73	Section 3.7.1 p.15	"Where HR (hazard ratio) is the ratio of median overall survival of Placebo and Rivoceranib* group."	"where HR (hazard ratio) is the ratio of median overall survival of denotes the hazard ratio for Rivoceranib group relative to Placebo group. "	Clarify language in the protocol.
Section 8.1.3 p.74	Section 3.7.3 p.16	"325 events (413 subjects) are needed."	" a total of 325 events (413 subjects) are needed to provide approximately 80% power for Overall Survival. "	Clarify language in the protocol.
Section 8.3.2 p.75	Section 4.1 Section 4.2 Section 4.3 Section 4.4 p.17	"ITT set consists of data from all subjects who are randomized." "The analysis for primary endpoint, OS and the secondary endpoints of PFS and ORR will be conducted in the ITT set." "Safety set consists of data from all subjects who received at least one dose of Rivoceranib or placebo." "The FAS will be used for all efficacy analyses." "The PPS will be used for all efficacy analyses."	"ITT set consists of data from all subjects who are randomized into the study. " " The analysis The ITT set will be used for the primary efficacy analyses endpoint, OS and the secondary endpoints of PFS and ORR will be conducted in the ITT set. " "Safety set consists of data from all subjects in the ITT population who received at least one dose of Rivoceranib or placebo." "The FAS will be used for all supportive efficacy analyses." "The PPS will be used for all supportive efficacy analyses."	Clarification that ITT set will be used for the primary efficacy analyses, and FAS and PPS will be used for supportive efficacy analyses.

Protocol v5.0 Location(s)	SAP Location(s)	Protocol v5.0 Language	SAP Language Changed from Protocol v5.0	Reason of Change
Appendix 2: Table 3 p.91	Section 5.1 Table 4 Table 5 p.18	Table title: Time Point Response	Table title: Time Point Response (subjects with target and non-target lesion) Added table 5: Time Point Response (subjects with non-target lesion only)	Clarified on the original table and added a table to define response for subjects with non-target lesion only.
Section 8.2.1 p.74 Section 8.3.4 p.76	Section 5.1.1 p.19 Section 7.5.2 p.29	“Overall Survival (OS): Time from randomization to death. Subjects alive or lost to follow-up at the end of study (EOS) are censored.”	“Overall Survival (OS): Time from randomization to death. Subjects alive or lost to follow-up at the end of study (EOS) analysis cut-off point are censored at the date the subject was last known to be alive. ”	Clarified overall survival censoring.
Section 8.2.2 p.74 Section 8.3.5 p.76	Section 5.1.2 p.19 Section 7.5.3 p.30	“Subjects alive and free of progression at the end of study (EOS) are censored.”	“Subjects alive and free of progression at the end of study (EOS) are censored at the last tumor assessment date when alive and free of progression were known. ”	Clarified progression free survival censoring.
Section 8.3.5 p.76	Section 5.1.2 p.19	“Progression Free Survival (PFS): Time from randomization to either radiological progression (determined by the central imaging analysis facility) or death from any cause.”	Centrally imaging results will determine the subject's best tumor response and time of progression according to RECIST 1.1. for PFS, ORR and DCR. In addition, supportive tumor response and progression will be analyzed based on investigator assessment.	Added supportive tumor response and progression analyses based on investigator assessment.
Section 8.3.4 p.76	Section 7.5.2 p.29	“The comparison of OS between the two treatment groups will be performed with a stratified log-rank	“The comparison of OS between the two treatment groups will be performed with a log-rank test stratified on the randomization stratification variables	Due to the occurrence of several very small strata for non-measurable subjects, it is not meaningful to conduct

Protocol v5.0 Location(s)	SAP Location(s)	Protocol v5.0 Language	SAP Language Changed from Protocol v5.0	Reason of Change
		test at the two-sided alpha=0.05 level of significance.”	[Geographic region (Asia vs. North America/Europe) , Prior ramucirumab treatment (Yes vs. No) , and Treatment therapy line (3rd vs. ≥ 4th)] at the two-sided alpha=0.05 level of significance.”	stratified analyses using all four randomization stratification variables. The measurable vs. non-measurable stratification criteria will not be utilized in all stratified analyses.
Section 8.3.4 p.77	Section 7.5.2 p.29-30	“For the ORR (CR or PR), ...Response in both treatment groups will be compared with the Cochran-Mantel-Haenszel test stratified by the randomization stratification factors.”	“ORR will be analyzed using the Cochran-Mantel-Haenszel test stratified by the randomization stratification factors Geographic region (Asia vs. North America/Europe) , Prior ramucirumab treatment (Yes vs. No) , and Treatment therapy line (3rd vs. ≥ 4th) .”	Due to the occurrence of several very small strata for non-measurable subjects, it is not meaningful to conduct stratified analyses using all four randomization stratification variables. The measurable vs. non-measurable stratification criteria will not be utilized in all stratified analyses.
Section 8.3.4 p.82	Section 5.1.2 p.19	Entire table: Table 8. PFS censoring rule	Entire table: Table 8. PFS censoring rule . Subjects alive and free of progression are censored at the last tumor assessment date when alive and free of progression were known.”	Scenarios in Table 8 in the protocol is redundant and not entirely accurate, so the entire table is removed and replaced by the censoring guideline described in this SAP. Specifically, death for any cause should always be a PFS event.

[figure not shown]
* Note: For purposes of this SAP, Rivoceranib will be used as the nonproprietary name throughout the document. Apatinib was formerly used in the protocol. In addition, grammatical and typographical changes are not included in the table.

